14.11.16.2. Part B

No.	Population	IDSL / Example Shell	Title	Programming Notes	Deliverable
Subject Disposition					
32.	Screened	ES7	Part B: Listing of Reasons for Screen Failures		Part B SAC
33.	Screened	ES9	Part B: Listing of Subjects who were Rescreened		Part B SAC
34.	Enrolled	ES2	Part B: Listing of Reasons for Study Withdrawal		Part B SAC
35.	Randomized	BL1	Part B: Listing of Subjects for Whom the Treatment Blind was Broken		Part B SAC
36.	ITT	SD2	Part B: Listing of Reasons for Study Treatment Discontinuation		Part B SAC
37.	Randomized	TA1	Part B: Listing of Planned and Actual Treatments		Part B SAC
Protocol Deviations					
38.	Enrolled	DV2	Part B: Listing of Important Protocol Deviations		Part B SAC

No.	Population	IDS / Example Shell	Title	Programming Notes	Deliverable
39.	Enrolled	IE3	Part B: Listing of Subjects with Inclusion/Exclusion Criteria Deviations		Part B SAC
Populations Analysed					
40.	Enrolled	SP3	Part B: Listing of Subjects Excluded from Any Population		Part B SAC
Demographic and Baseline Characteristics					
41.	Randomized	DM2	Part B: Listing of Demographic Characteristics		Part B SAC
42.	Randomized	DM9	Part B: Listing of Race		Part B SAC
Medical Conditions					
43.	Safety	MH2	Part B: Listing of Current and Past Medical Conditions		Part B SAC
Concomitant Medications					
44.	Safety	CP_CM3	Part B: Listing of Prior and Concomitant Medications		Part B SAC
45.	Safety	CP_CM3	Part B: Listing of Prior and Concomitant Osteoarthritis Medications	OA con-meds are captured on a specific CRF page	Part B SAC
Exposure					
46.	Safety	EX3	Part B: Listing of Exposure Data	Include number of injections received	Part B SAC
Adverse Events					
47.	Safety	AE8CP	Part B: Listing of All Adverse Events		Part B SAC
48.	Safety	AE7	Part B: Listing of Subject Numbers for Individual Adverse Events		Part B SAC
49.	Safety	AE2	Part B: Listing of Relationship Between Adverse Event System Organ Classes, Preferred Terms, and Verbatim Text		Part B SAC
Serious and Other Significant Adverse Events					
50.	Safety	AE8CPa	Part B: Listing of Serious Adverse Events (Fatal and Non-Fatal)		Part B SAC
51.	Safety	AE14	Part B: Listing of Reasons for Considering as a Serious Adverse Event		Part B SAC

CONFIDENTIAL

207804

No.	Population	IDSL / Example Shell	Title	Programming Notes	Deliverable
52.	Safety	AE8CP	Part B: Listing of Adverse Events Leading to Withdrawal from Study / Permanent Discontinuation of Study Treatment		IA3, Part B SAC
53.	Safety	AE8CP	Part B: Listing of Other Significant Adverse Events		Part B SAC
Vital Signs					
54.	Safety	VS4	Part B: Listing of Vital Signs of Potential Clinical Importance		Part B SAC
55.	Safety	VS4	Part B: Listing of All Vital Signs Data for Subjects with Any Value of Potential Clinical Importance		Part B SAC
Laboratory: All					
56.	Safety	LB5	Part B: Listing of Laboratory Values of Potential Clinical Importance		IA3, Part B SAC
57.	Safety	LB5	Part B: Listing of All Laboratory Data for Subjects with Any Value of Potential Clinical Importance		IA3, Part B SAC
58.	Safety	LB14	Part B: Listing of Laboratory Data with Character Results		Part B SAC
59.	Safety	UR2A	Part B: Listing of Urinalysis Data for Subjects with Any Value of Potential Clinical Importance		Part B SAC
ECG					
60.	Safety	EG3	Part B: Listing of ECG Values of Potential Clinical Importance		Part B SAC
61.	Safety	EG3	Part B: Listing of All ECG Values for Subjects with Any Value of Potential Clinical Importance		Part B SAC
62.	Safety	EG5	Part B: Listing of Abnormal ECG Findings		Part B SAC
63.	Safety	EG5	Part B: Listing of All ECG Findings for Subjects with an Abnormal ECG Finding		Part B SAC

14.11.17. ICH Conditional Listings

The following listings will only be produced if a liver event is observed within the trial.

14.11.17.1. Part A

No.	Population	IDSL / Example Shell	Title	Programming Notes	Deliverable
Hepatobiliary (Liver)					
64.	Safety	MH2	Part A: Listing of Medical Conditions for Subjects with Liver Stopping Events	Conditional on liver event being seen	Part A SAC
65.	Safety	SU2	Part A: Listing of Substance Use for Subjects with Liver Stopping Events	Conditional on liver event being seen	Part A SAC

14.11.17.2. Part B

No.	Population	IDSL / Example Shell	Title	Programming Notes	Deliverable
Hepatobiliary (Liver)					
66.	Safety	MH2	Part B: Listing of Medical Conditions for Subjects with Liver Stopping Events	Conditional on liver event being seen	Part B SAC
67.	Safety	MH2	Part B: Listing of Substance Use for Subjects with Liver Stopping Events	Conditional on liver event being seen	Part B SAC

14.11.18. Non-ICH Listings

14.11.18.1. Part A

No.	Population	IDSL / Example Shell	Title	Programming Notes	Deliverable [Priority]
Substance Use					
68.	Safety	SU2	Part A: Listing of Substance Use	Include columns: Smoking history, Currently Smoke, Last Smoked, Drink Alcohol, Units per Week, Currently using Illicit Drugs	Part A SAC
Pharmacokinetics					
69.	PK	PK07	Part A: Listing of Serum GSK3858279 Concentration-Time Data (ng/mL)		Part A SAC
70.	PK	PK13	Part A: Listing of Derived Serum GSK3858279 Pharmacokinetic Parameters	Add a footnote saying that NQ means non-quantifiable and LLQ=100 ng/mL	Part A SAC
CCI					

No.	Population	IDSL / Example Shell	Title	Programming Notes	Deliverable [Priority]
Pharmacodynamic					
72.	Safety	PK07	Part A: Listing of Free & Total CCL17 in Serum Concentration-Time Data (pg/mL)	Including Percentage Inhibition/Fold Increase Add a footnote saying that NQ means non-quantifiable and Free CCL17 LLOQ=2.93 pg/mL and Total CCL17 LLOQ=13.11 pg/mL.	Part A SAC
73.	Safety	PK13	Part A: Listing of Derived Free CCL17 in Serum Target Engagement Parameters		Part A SAC
74.	Safety	PK13	Part A: Listing of Derived Total CCL17 in Serum Target Engagement Parameters		Part A SAC
75.	Blister	PK07	Part A: Listing of Free & Total CCL17 in Blister Fluid Concentration-Time Data (pg/mL)	Including Blister/Serum Ratio	Part A SAC
76.	Safety	IMM2	Part A: Listing of Immunogenicity		Part A SAC
Biomarker					
77.	Biomarker	BIO_L1	Part A: Listing of Immune Cell Phenotypes		Part A SAC

14.11.18.2. Part B

No.	Population	IDSL / Example Shell	Title	Programming Notes	Deliverable
Substance Use					
78.	Safety	SU2	Part B: Listing of Substance Use	Include columns: Smoking history, Currently Smoke, Last Smoked, Drink Alcohol, Units per Week, Currently using Illicit Drugs	Part B SAC

No.	Population	IDS / Example Shell	Title	Programming Notes	Deliverable
Pharmacokinetics					
79.	PK	PK07	Part B: Listing of Serum GSK3858279 Concentration-Time Data (ng/mL)	Add a footnote saying that NQ means non-quantifiable and LLOQ=100 ng/ml	Part B SAC
80.	PK	PK13	Part B: Listing of Model-Derived Serum GSK3858279 Pharmacokinetic Parameters	Add a footnote saying that "All Pharmacokinetic parameters were calculated using a model based post-hoc analysis".	Part B SAC
Pharmacodynamic					
81.	Safety	PK07	Part B: Listing of Free & Total CCL17 in Serum Concentration-Time Data (pg/mL)	Add a footnote saying that LLOQ means lower limit of quantification and ULOQ means upper limit of quantification. LLOQ for free CCL17= 2.93 pg/mL. LLOQ for total CCL17= 13.11 pg/mL. ULOQ for free CCL17= 3600 pg/mL. ULOQ for total CCL17= 50000 pg/mL.	Part B SAC
82.	Safety	PK13	Part B: Listing of Derived Free CCL17 in Serum Target Engagement Parameters	Including Percentage Inhibition/Fold Increase. Add a footnote saying "All Target Engagement parameters were calculated using a model based post-hoc analysis.". .	Part B SAC
83.	Safety	PK13	Part B: Listing of Derived Total CCL17 in Serum Target Engagement Parameters	Add a footnote saying "All Target Engagement parameters were calculated using a model based post-hoc analysis.". .	Part B SAC
84.	Safety	IMM2	Part B: Listing of Immunogenicity	For IA3, include only participants with at least one positive confirmation assay result.	IA3, Part B SAC
Primary Efficacy					
85.	ITT	EFF_L01	Part B: Listing of Average and Worst Knee Pain Intensity	Include the number of records which make up the average	IA1, IA2, Part B SAC

CONFIDENTIAL

207804

No.	Population	IDS / Example Shell	Title	Programming Notes	Deliverable
CCI					
COVID-19					
88.	Randomized	PAN7	Part B: Listing of All Subjects with Visits and Assessments Impacted by COVID-19 Pandemic		Part B SAC

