9.4.5. Interim Analyses

Part A: No formal interim statistical analyses are planned. However, dose escalation meetings will occur at a relevant timepoint after each dose level; including between Parts A and B.

The decision to proceed to the next cohort, and next dose strength to be studied, will be made by the DEC based on assessment of safety and serum GSK3858279 pharmacokinetic data obtained in all participants at the prior dose level. Individual safety data (AEs, laboratory safety tests, ECGs and vital signs) will be reviewed. In addition, un-blinded preliminary PD data may be reviewed by the DEC during the study; where the GSK biology lead will join the DEC in these discussions. Once sufficient safety, PK and target engagement data is collected from the top IV dose and SC cohorts, a data review will take place and a decision to proceed with Part B of the study may be made. Further details are included in the DEP.

Unblinded data from Part A may be reported out in full following the last subject last visit in this part of the study and prior to the conclusion of Part B.

Part B: An interim analysis will occur once approximately 20 participants have completed the Week 4 assessment. A second interim analysis and an unblinded sample size re-estimation may occur prior to enrolling the 50th participant, where the sample size could be decreased to a minimum of 20 or increased to a maximum of 80 participants.

Additional interim analyses may occur in order to inform internal decision making. Full details of all interim analyses will be prospectively outlined in the interim analyses charter.

At the interim analyses, treatment group level, efficacy, safety, PK, TE, rescue medication and ADA data may be reviewed by a list of people included in the IA charter, including the Project Leader and Independent Internal Review Board and internal governance boards as required. Individual participant data may be reviewed at the request of the project leader, but subject identification numbers will be removed to maintain the blind.

If there are interactions with regulatory agencies, any interim data presented will be at the treatment group level unless individual participant data is requested. Unblinded safety information may be presented at an individual level

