5.2. Study Treatment Display Descriptors

In the Tables, Listings and Figures (TLF), treatment should be presented with placebo first, then in order of increasing dose by route of administration within each part.

Part A: Treatment group descriptions			
RandAll NG		Data displays for reporting	
Code	Description	Description	Order in TLF
A	0.1 mg/kg IV GSK3858279	0.1 mg/kg IV GSK3858279	2
B	0.3 mg/kg IV GSK3858279	0.3 mg/kg IV GSK3858279	3
C	1 mg/kg IV GSK3858279	1 mg/kg IV GSK3858279	4
D	3 mg/kg IV GSK3858279	3 mg/kg IV GSK3858279	5
E	10 mg/kg IV GSK3858279	10 mg/kg IV GSK3858279	6
F	SC GSK3858279	3 mg/kg SC GSK3858279	7
P	Placebo	Placebo	1

Part B: Treatment group descriptions			
RandAll NG		Data displays for reporting	
Code	Description	Description	Order in TLF
G	240 mg SC GSK3858279	240 mg SC GSK3858279	2
P	Placebo	Placebo	1

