14.6. Appendix 6: Derived and Transformed Data

14.6.1. General

Subject Number

 Participants will be assigned a unique identification number: study number concatenated subject ID number. In the case of a subject being enrolled multiple times, the first subject ID number will be used. For more details, see the AR data set specifications. Listings will include both subject ID and unique subject ID.
Multiple measurements at one analysis time point

 Mean of the measurements will be calculated and used in any derivation of summary statistics but if listed, all data will be presented. Participants having both high and low values for Normal Ranges at any post-baseline visit for safety parameters will be counted in both the High and Low categories of "Any visit post-baseline" row of related summary tables. This will also be applicable to relevant Potential Clinical Importance summary tables.
Study day

 Calculated as the number of days from first dose date: 
 ref date = missing → study day = missing ref date < first dose date → study day = ref date – first dose date ref date ≥ first dose date → study day = ref date – (first dose date) + 1
Nominal Visit Day

 Nominal Visit Days were updated in protocol, however some visits may be recorded under the incorrect visit number/label for Part A only: 
 Day 112 and Day 113 will be collapsed under the Nominal Visit: Day 113. Day 140 and Day 141 will be collapsed under the Nominal Visit: Day 141.

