14.6.5. Immunogenicity

A seed (5315) will be generated using code as outlined in Section [14.9.2](#). This will be saved in the refdata area.

- Using the generated seed, random numbers will be generated for all subjects that exist in the imgen dataset.
- These subjects will be ordered based on the random number and letters assigned sequentially (i.e. the patient with the smallest random number was ‘a’, the next patient ‘b’ and so on).

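### The SAP schedules participant listings with subject IDs at Part B interim analyses, although the protocol requires IDs to be removed, and it makes no interim exception

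*SAP*

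**What the plan says.** **Protocol.** Section 9.4.5 provides for Part B interim review of data at treatment-group level by people named in the interim charter. Individual participant data may be looked at if the project leader asks, "but subject identification numbers will be removed to maintain the blind". Section 6.3.2 lets the Interim Data Review Committee and senior sponsor leadership see unblinded interim data, but only as 9.4.5 describes, so the ID rule applies to them too. A separate paragraph of 9.4.5, on regulatory interactions, allows unblinded safety information to be shown for individuals.

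**SAP, what is delivered.** Section 14.11.18.2 gives Listing 85, "Part B: Listing of Average and Worst Knee Pain Intensity", the delivery tag "IA1, IA2, Part B SAC". Listing 84 (immunogenicity) in the same section is tagged for IA3. In 14.11.16.2, Listings 52, 56 and 57 are tagged for IA3; Listing 57 is "Part B: Listing of All Laboratory Data for Subjects with Any Value of Potential Clinical Importance".

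**SAP, what a listing contains.** Section 14.6.1 says "Listings will include both subject ID and unique subject ID". Section 5.2 says "In the Tables, Listings and Figures (TLF), treatment should be presented with placebo first".

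**SAP, masking.** Section 3.1 describes dummy IDs or group-level display in its paragraph on the two blinded safety reviews. Section 10.3.2 anonymises participants for safety reviews 1 and 2, by the letter coding in 14.6.5. Section 3.1 leaves further interim detail to the Interim Analysis Charter.

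**The concern.** The protocol makes individual interim data an exception, on request and with IDs stripped. The SAP makes participant listings a standing part of three interim deliveries, under a general rule that puts two identifiers on each listing. A programmer who follows the SAP literally produces an output that the protocol says reviewers should not have.

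If the listings also show treatment, a reader could tie a numbered participant to an arm while the trial is running. The co-primary endpoints are self-reported pain. SAP 4.2 has important protocol deviations reviewed before unblinding, and those deviations decide the Per Protocol population used in the supportive analysis. Knowledge of allocation among sponsor staff would weaken that safeguard.

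**Working it through.** No design figure is involved, so the check is a comparison of texts plus one subtraction.

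**Step 1. Part B participant listings with an interim tag (SAP 14.11.16.2 and 14.11.18.2).**

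| Listing | Content | Interim tag | Instruction to mask IDs |
|---|---|---|---|
| 52 | AEs leading to withdrawal or discontinuation | IA3 | none |
| 56 | Laboratory values of potential clinical importance | IA3 | none |
| 57 | All laboratory data for participants with such a value | IA3 | none |
| 84 | Immunogenicity | IA3 | none |
| 85 | Average and worst knee pain | IA1, IA2 | none |

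Five visible listings carry an interim tag and none has an instruction to remove or replace IDs. No participant listing is visibly tagged for IA4. Interim-specific programming notes were possible: Listing 84 has one, "For IA3, include only participants with at least one positive confirmation assay result", but it restricts who is listed, not how they are identified.

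**Step 2. Does any SAP masking rule reach IA1 to IA4?** The text in 3.1, 10.3.2 and 14.6.5 is tied to the two safety reviews. Section 14.6.1 is unconditional. So in the SAP the general ID rule governs the interim listings.

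**Step 3. Would treatment appear?** Protocol 9.4.1 has pain scores listed by participant and intervention. SAP 5.2 sets how treatment is presented and names listings among the displays. SAP 7.1.2 says the listing is by participant and attaches treatment only to the summary. The Listing 85 entry is silent, and its layout (shell EFF_L01) is in a separate shells document. A treatment column is a strong inference, not a stated fact.

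**Step 4. Who might be affected at IA2?** SAP 7.1.5.1 places IA2 at about 45 randomised, estimated to be when 28 have reached Week 8.

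- Not yet at Week 8: 45 − 28 = 17, or 17/45 = 38%.
- Share of the planned total randomised by then: 45/50 = 90%; of the maximum: 45/80 = 56%.

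These count people who could be on a listing, not allocations disclosed. The 17 may include some who have already discontinued, and IA2 itself is optional. IA1 is triggered by 20 participants at Week 4, but the SAP does not say how many would then be randomised. It gives no timing for IA3.

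**Step 5. Is Listing 85 needed at IA1 and IA2?** Section 14.11.14.1 already delivers Table 6.01 (completeness of pain data by arm) and Tables 6.02 and 6.03 (summary and Bayesian analysis of average pain) at both. Average pain is the IA1 endpoint (SAP 7.1.5.1), and its Week 8 SD drives the sample size re-estimation (SAP 2.3).

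**The case against.** The strongest reply is that a delivery tag shows what is programmed, not who reads it. The SAP names no recipients. Protocol 9.4.5 governs the review and already requires IDs to be removed, and the charter may mask IDs or confine the listings to an unblinded programming team. This stands as far as the consequence goes: a reader might infer that sponsor leaders would learn individual allocations, and the documents do not support that. It does not remove the conflict between the two texts.

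Other replies also have weight:

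- **Safety data.** The allowance in protocol 9.4.5 for individual unblinded safety information may partly cover Listings 52, 56, 57 and 84, although it sits in the paragraph on regulatory interactions. It does not cover Listing 85, which is efficacy data.
- **Content of Listing 85.** Its programming note asks for the number of records behind each average, so it appears to show averaged scores and not raw daily entries.
- **Bias pathway.** Participants enter pain in a digital tool, and the study is participant- and investigator-blinded. The Per Protocol exclusions are largely prespecified counts, and that analysis is supportive, run only if the population is 50 to 90% of ITT. Nothing says that interim reviewers classify deviations or handle queries. The ITT primary analysis does not depend on those decisions.
- **The printed seed.** SAP 14.6.5 states "A seed (5315) will be generated using code as outlined in Section" 14.9.2, and a reader might infer that anyone holding the SAP could rebuild the dummy key. The printed code generates seeds. The function that draws the random numbers for participants and the order of records in the dataset are not given, so this is not shown. The coding also belongs to the safety reviews, not to the interims.

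**Conclusion.** The point holds as a conflict between SAP and protocol that should be reconciled. Followed literally, SAP 14.6.1 and the delivery tags give five participant listings with subject IDs at IA1 to IA3, against a protocol rule that IDs be removed and individual data be seen only on request. Listing 85 is the clearest case.

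The possible consequence is a link between participant and arm for interim reviewers while, on the SAP's estimate, about 17 of some 45 randomised participants had not yet reached Week 8 at IA2. That rests on three assumptions: the listings show treatment, they reach reviewers as programmed, and the charter adds no masking. The charter and shells are not supplied, so none of these can be settled here. A breach of the blind is not demonstrated, and any effect on the primary ITT analysis would be indirect.

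**What to change.** Add to SAP 14.6.1 (or 3.1) that any listing delivered to reviewers at a Part B interim analysis carries dummy IDs only, with neither subject ID nor unique subject ID, and tag Listings 52, 56, 57, 84 and 85 to match. For Listing 85 the alternative is to drop the IA1 and IA2 tags, because Tables 6.01 to 6.03 already supply the group-level data for those decisions.

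The cost is SAP wording and one programming step, with no new data. The downside is that an interim query about an individual has to go through the unblinded key holder.
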